E1574-P

NCT02374463

Improving Balance and Mobility (MMBI)

Document date: February 13, 2020

Study protocol and analysis plan

Every 5 seconds an older American falls, yielding annual costs over \$30 billion for fall-related injuries. Beyond financial concerns, for adults over the age of 65, falls are the leading cause of injurious death, non-fatal injuries, and hospital admissions for trauma. With more than 60% of current veterans over the age of 55, preventing falls and fall related injuries has become a major concern for the VA health system. Despite a wide variety of research into fall prevention, the state of the art fall prevention programs reduce falls by only 30%, suggesting more research is required. Falls are multifactorial in origin with a failure to negotiate environmental hazards, muscle weakness, impaired postural control, and gait and balance deficits being among the top contributors to falls in older adults. The multifactorial origins of falls requires a multimodality approach to effectively reduce falls. Derivations of t'ai chi ch'uan (Tai Chi) have become popular in western society as low-impact balance and fitness programs suitable for older adults, and Tai Chi is the only modality specifically recommended by the CDC for fall prevention. However, while previous research has demonstrated that Tai Chi may be effective at improving balance and general lower body strength, there are questions concerning its actual effectiveness to prevent falls. Some Tai Chi program also have low adherence rates resulting in a decreased effectiveness. The slow choreographic weight shifts central to Tai Chi may improve some aspects of balance and may provide a general lower body strengthening but do little to improve gait, negotiation of environmental hazards, nor dynamic balance recovery following perturbation. Targeted interventions focused on improving stepping and walking ability may be even more effective at improving balance and mobility. Preliminary studies demonstrate that our novel progressive group multimodal balance intervention (MMBI), focusing on lateral movements, lower extremity strengthening and dynamic obstacle negotiation, can improve balance, gait and strength in older adults at high risk for falls. It is our overall hypothesis that both MMBI and Tai Chi interventions will improve muscle strength and balance, but we hypothesize that MMBI will result in larger improvements in gait, balance and lower extremity strength in older veterans at high risk for falls and thereby result in fewer falls and lower fall rates in the MMBI group.

To test our hypotheses, we propose to conduct a pilot randomized clinical trial with the following specific aims:

**Specific Aim 1:** To compare the effectiveness and adherence to 6 months of a novel Multi Modal Balance Intervention (MMBI) program versus Tai Chi exercise training to improving balance [Four-Square Step Test (FSST) and Functional Gait Assessment Tests (FGA)], gait (spatio-temporal gait parameters), lower extremity isometric strength (Biodex) and mobility fitness (distance covered during a 6 minute walk) pre and post intervention in older veterans at increased risk for falling.

H1: MMBI will result in larger improvements than Tai Chi in balance, gait, lower extremity strength, and mobility fitness.

H2: MMBI will have a higher adherence rate than a Tai Chi exercise program

[figure not shown]
**Specific Aim 2 (exploratory):** To determine and compare the effectiveness of 6 months of MMBI versus Tai Chi exercise training to prevent falls and reduce the number of serious falls in older veterans at increased risk for falling.

H1: MMBI will result in greater decreases in serious falls than Tai Chi and this will be maintained for 6 months following the completion of the exercise program.

Background and Significance:

Falls are complex and multi-factorial in origin with numerous deficits including impaired balance, decreased postural control, muscle weakness, sensory changes, and a composite inability to successfully negotiate environmental hazards and obstacles (see conceptual model). The majority of falls occur during walking, with incident slips and trips, such that targeted interventions focused on stepping and walking ability may be more effective at improving dynamic balance and reducing falls. Older adults are particularly vulnerable to falls during lateral or diagonal movements. While the mechanism of lateral instability remains under investigation, it is reasonable to suspect deterioration in the hip abductor muscles as a major contributor to their difficulty in maintaining and regaining balance.

Interventions to reduce fall risk require a multi-faceted approach. Well established components include review of medications, sensory exams, home safety inspection, etc. The optimal exercise component, however, remains uncertain (see Cochran review 2012). Tai Chi is recommended by the CDC to prevention falls in older adults and this endorsement widely influences health care policy. Tai Chi improves balance by 12% and may reduce fall rates by perhaps 28% but does not reduced the risk of falling (Cochran). The slow dynamic weight shift that occurs during Tai Chi may generally improve balance, decrease fall risk, and provide general lower body strengthening. However Tai Chi may not sufficiently improve gait and dynamic mobility and nor effectively improve obstacle negotiation, one of the most common scenarios for injurious falls. A multimodal balance intervention (MMBI) that addresses these deficiencies may be more effective than Tai Chi in reducing fall risk. However, there are few studies comparing Tai Chi with another active intervention. Conceptual model

Our work has demonstrated that, compared to non-fallers, older adults with a history of falls have increased fatty depots in their hip abductor muscles and decreased hip abductor strength. A high degree of abductor fat correlates with greater gait variability and fall risk in older adults. This leads us to propose that, in addition to the established age-associated changes in leg flexors and extensors, similar changes in hip abductor muscles may hinder balance and mobility function. Disuse may contribute to these changes as older adults tend not to engage in activities that require lateral movement. As shown in our conceptual model, a group balance and strengthening program focused on dynamic use of the hip abductors through lateral and diagonal stepping and obstacle negotiation, walking, and lower extremity strengthening may be more effective at improving balance and mobility and reducing falls in older veterans. This research directly benefits veterans as it may lead to new and effective interventions that could reduce fall risk, injury-related hospitalization and death in older veterans. MMBI is also readily exportable to the community and with minimal resources could be widely implemented at other VAs as part of standard of care, similar to MOVE!

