### Methods/Study Procedures:

Approach: We will enroll 56 older community dwelling veterans (age > 65 years) with a fall in the past year and evidence of balance dysfunction (FSST > 10 seconds). Our preliminary findings suggest that those with higher FSST benefit the most from MMBI. After baseline testing, individuals will be randomized to either MMBI or to a Tai Chi intervention. All participants will participate in a group exercise class in their assigned intervention for 1 hour, 3 times per week for 24 weeks. To promote camaraderie and accountability among subjects they will be enrolled in intervention cohorts of 8 to 10 subjects. At randomization subjects will be stratified first by gender then by FSST. Assessments will occur at baseline and after completion of the intervention and will include balance, mobility and fall risk, lower extremity strength, and muscle composition (total body DXA scan, hip and thigh CT scan). All participants will be followed from initial enrollment until 6 months after completion of the post-intervention testing (6 months follow up) utilizing calendar diaries, post-cards and monthly phone calls from the study coordinator to determine the number of falls, near falls, injuries and fall related medical visits.

Recruitment and Screening: A variety of methods will be used to recruit older veterans with a history of a fall in the last year, including the Baltimore GRECC subject recruitment registry, advertisements, provider referrals, community outreach, outpatient clinics and the emergency department at the VAMHCS. The use of multiple recruitment strategies will allow us to maximize our outreach to a diversity of veterans including those who have yet to seek routine care at the VA. A fall will be defined as any event that resulted in a person coming to rest unintentionally on the ground or other lower level. Prospective studies have demonstrated that older adults with a history of falls are more likely to experience subsequent falls. Exclusion criteria will include: dementia, unstable angina, poorly controlled hypertension, active substance abuse, poorly controlled diabetes, progressive neurodegenerative disease, and any other major orthopedic or health condition that would limit ability to safely exercise (see human subjects section for more

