details). Interested individuals will initially undergo a telephone screen by the project coordinator to assess eligibility for the study using our inclusion/exclusion criteria. Potential participants who pass the phone screen will be invited to our facility. After informed consent, a history and physical will be performed. Based on prior studies we anticipated that 20 to 30% of those brought in for the screening evaluations will not qualify for the study (screening failures).

After the completion of all screening tests eligible participants will be scheduled for baseline testing at the Baltimore GRECC and VAMHC Human Performance Laboratory consisting of: 1) balance testing (Four-square step test), 2) mobility and fall risk assessment (functional gait assessment, clinical gait assessment and gait variability on a GAITrite and 6 minute walk), 3) questionnaires (falls efficacy and ABC) 4) lower extremity isometric strength testing (Biodex), and 6) total body DXA scan, and a CT scan of the abdomen, hips and thighs for determination of lower extremity and core muscle composition. All testing will be conducted by individuals that are blinded to group assignment and not involved with group training.

After completion of baseline testing the veterans will be randomized to either MMBI or a Tai Chi intervention. The MMBI and Tai Chi intervention sessions will be held at different times of the day to minimize cross-contamination between the two groups, with time alternating with different cohorts to minimize any inadvertent training effect due to time of day.

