Statistical Analysis: Data analyses will be performed using SAS. We will first perform an exploratory analysis to look for extreme values to make sure they are not the result of data entry error. All analyses will be conducted using the intention-to-treat principle. Statistical significance will be at an alpha of 0.05 (two-tailed). Demographic and clinical characteristics at baseline will be summarized with standard descriptive statistics.

For aim 1, to compare changes (defined as 24-week value minus baseline value) in mobility, balance and strength between our two groups (tai chi and MMBI) after 24 weeks of intervention we will use ANOVA for all continuous outcome measures (change=group).

For Aim 2 We will use Poisson regression (or, if the data are overdispersed Quasipoisson or negative binomial regression) to compare the number of falls in our two experimental groups. This methodology has been employed in the LiFe trial and other studies.

Project time line: Prior to the start of the funding, we will obtain regulatory approvals from the IRB and VA R&DC. We will recruit 3 sets of intervention cohorts. Recruitment and baseline testing of the first cohort will start at the start of the funding period and they will enter intervention at month 3. While this first cohort is undergoing intervention we will recruit and perform baseline testing on the second cohort who will enter the intervention approximately 6 months after the start of the study. Post intervention testing on the first cohort will commence at 9 months. Recruitment for the third cohort will be done while the second cohort is in intervention and the third cohort will start their intervention at 9 months. During months 21 to 24 we will perform data analysis, and start writing manuscripts. We have used a similar strategy of staggered cohorts in prior studies. The study will be completed in a two years.

Anticipated Results and Alternate Findings: While we do not anticipate that Tai Chi will result in larger improvements in balance and falls than MMBI it is possible. The strength, balance, and gait tests that we are performing allow us to evaluate the contribution each makes to improving balance. This information can be used to design a future larger study aimed at decreasing falls.

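### Aim 2 names no fall count taken before randomisation and no covariate: the between-arm fall comparison is valid, but a cheap gain in precision is left unspecified and H1 is loosely worded (minor)

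*Combined protocol and SAP*

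**What the plan says.** Specific Aim 2 is labelled exploratory. Its H1 reads: "MMBI will result in greater decreases in serious falls than Tai Chi", and adds that the advantage will last for six months after the programme ends. The opening section states the same expectation as a contrast between arms: the intervention should "thereby result in fewer falls and lower fall rates in the MMBI group".

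Under Methods/Study Procedures, participants are veterans "with a fall in the past year and evidence of balance dysfunction". Randomisation is stratified by gender and then by the Four-Square Step Test (FSST). At screening, "After informed consent, a history and physical will be performed"; its content is not described. The baseline tests listed next cover balance, gait, walking distance, falls efficacy and balance confidence, strength, DXA and CT. The number of earlier falls is not among them. The Aim 2 outcome text has participants report falls that occur after enrollment.

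The Sample Size section defines the Aim 2 outcome as the fall rate and the proportion of fallers during the intervention. The Statistical Analysis uses Poisson regression, or quasi-Poisson or negative binomial if overdispersed, "to compare the number of falls in our two experimental groups". It names no covariate.

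**The concern.** A decrease implies a before and an after, and for falls the plan specifies only the after. As a yes/no item, the past-year fall is the same for everyone and carries no information within the trial. The number of past-year falls does vary between people, and it is a natural predictor of later falls. The plan points that way when it justifies the entry criterion: "Prospective studies have demonstrated that older adults with a history of falls are more likely to experience subsequent falls".

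The plan intends to use its results to power a larger trial. With 20 or 28 people per arm, a few recurrent fallers in one arm can shift the estimated rate ratio noticeably. As written, the plan has no prior fall count with which to show or adjust for such an imbalance.

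**Working it through.** **1. The passages side by side.** The opening section, the outcome definition and the model all describe a contrast between arms. Only H1 uses the language of change. No change-from-baseline analysis of falls is planned, unlike Aim 1, which analyses the 24-week value minus baseline.

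**2. The plan's own figure.** The Sample Size section gives 90 per group for a 25% reduction (80% power, 5% alpha, 20% dropout). The two-sided Poisson formula is n = (1.960 + 0.842)² × (1/μ₁ + 1/μ₂) / (ln 0.75)². With 2.28 falls per person-year (the cited trial's controls) over one year, μ₁ = 2.28 and μ₂ = 1.71. Then n = 7.85 × (0.439 + 0.585) / 0.0828, which is about 97 to 98, or about 122 after dividing by 0.8. Over six months it is 195, or 243 after dropout. The base rate, exposure and dispersion behind 90 are not stated, so the figure is unverified but not shown to be wrong. Nothing below depends on it.

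**3. Why a pre-post change would mislead.** Let m be the yearly fall rate in the source population and k the dispersion (k = 1/gamma shape, assumed). If at least one past-year fall is required for entry, the mean drops afterwards with no treatment effect by (1 + km)^−(1 + 1/k), or e^−m when k = 0.

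| m per year | k = 0 | k = 0.5 | k = 1.5 |
|---|---|---|---|
| 1.66 | e^−1.66 = 19% | 1.83^−3 = 16% | 3.49^−1.67 = 12% |
| 2.28 | e^−2.28 = 10% | 2.14^−3 = 10% | 4.42^−1.67 = 8% |

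The artefact is therefore about 8% to 19%.

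**4. Gain from using the count as a covariate.** The simulation draws gamma-distributed rates (shape 1 or 2), a Poisson past-year count kept only if it is at least 1, and a Poisson six-month outcome with no treatment effect. It fits Poisson regression with and without log(past-year falls). The gain is 1 − (SD adjusted / SD unadjusted)² for the log rate ratio.

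- Source rate 2 per year, 28 per arm, shape 1: 1 − (0.281/0.317)² = 21%. Shape 2: 1 − (0.290/0.310)² = 12%. A repeat with new draws gave 22% and 14%.
- Source rates 1.66 and 2.28, the range in the Sample Size section: 7% to 27% at 28 per arm and 7% to 26% at 20 per arm.
- Lower rate: selection raises the enrolled rate. At a source rate of 2 and shape 1, one third of people have no past-year fall, with mean rate 0.667, so the enrolled rate is (2 − 0.333 × 0.667)/0.667 = 2.67. At shape 2 it is (2 − 0.25 × 1)/0.75 = 2.33. Both exceed 2.28. The plan's preliminary study had 6 of 16 fallers in four months, or −ln(1 − 6/16) × 3 = 1.41 per year if Poisson. At an enrolled rate near 1.4 the gain is about 2% to 7%.
- Serious falls at 20% of all falls (an assumption; the plan does not define serious): about nil.
- No overdispersion: nil, because the past count then says nothing about the future rate.

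Across the all-falls settings with shape 1 to 2, allowing for simulation error, the range is roughly 2% to 28%.

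**5. Effect on power.** At 20 per arm, for a 25% reduction over six months, with k from 0.5 to 1.5 and source rates of 1.66 and 2.28, power moves from about 10–12% to about 12–14%.

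**The case against.** **Validity.** A randomised between-arm comparison of rates tests a relative reduction without any baseline count. This stands. A reader might infer from H1 that Aim 2 cannot be tested because no decrease can be computed. The documents do not support that: the opening section, the outcome definition and the model all specify a contrast between arms, and step 3 shows that a computed decrease would mislead.

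**Whether the count is collected.** A reader might also infer that prior falls go unrecorded. The history and physical is not described, and further detail on exclusions is referred to a human subjects section outside this document. The count is unspecified; it is not shown to be absent.

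**Existing control of fall risk.** FSST is already a stratifier. In the preliminary data it separated fallers from non-fallers (12.7 against 5.98 seconds, p = 0.009), and the plan links slow times to multiple falls. The simulation omits FSST and assumes perfect recall and no attrition, so it may credit the count with information already in hand. This stands as a reason to read the upper end of the range with caution.

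**Little at stake.** Aim 2 is exploratory, the plan concedes low power, and the overdispersed models would widen the interval when a few people fall often. This also stands. It lowers the priority of the change, but not the case for a nearly free covariate in a pilot whose estimates are meant to inform a larger trial.

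**Conclusion.** The point holds as a minor one. The plan specifies no fall count before randomisation and no covariate for the fall model, and H1 speaks of decreases where the analysis compares rates. The analysis itself is sound.

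The likely benefit is a reduction of roughly 2% to 28% in the variance of the all-falls log rate ratio. It rests on assumed gamma heterogeneity (shape 1 to 2), the fall rates in the documents, and 20 or 28 per arm, since the plan gives both 40 and 56 as the enrollment. It would be tempting to express the gain as a fixed equivalent in extra participants. The documents do not support that, because they give no dispersion, and the gain vanishes without overdispersion and is about nil for rare serious falls. The covariate does not rescue power for falls.

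**What to change.** - At the existing history-and-physical visit, before randomisation, record the number of falls in the past 12 months and the number that led to injury or medical care.
- Prespecify log(past-year falls) as a covariate in the Poisson, quasi-Poisson or negative binomial model for all falls. Do not analyse a pre-post change in falls.
- Reword H1 as a lower rate of serious falls on MMBI than on Tai Chi, in line with the opening section and the Aim 2 outcome definition, and state what counts as serious.
- If enrollment is complete, use any count already held in screening records, and reword H1 in any case.

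The cost is two questions at an existing visit, one model parameter and one reworded sentence. Twelve-month recall is imperfect, but an answer taken before randomisation cannot depend on the assigned arm, so recall error weakens the covariate without biasing the comparison.

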### Preliminary Studies:

We have assembled a highly qualified team of investigators with extensive expertise in performing exercise rehabilitation studies in older veterans. Seventeen older ( $75.6 \pm 4.5$ ) adults with a history of falls were recruited for a preliminary study utilizing MMBI. Subjects performed the intervention in our exercise facility 3 times/week for 16 weeks and were instructed in a home regimen to continue after completion of the center-based portion of the intervention. 16 out of 17 individuals completed all portions of the study with > 90% adherence to the protocol. Six of the 16 fell at least once during the 4 month study, and an additional six subjects reported at least 1 near fall. Four-square step times (FSST) in those who fell were significantly slower ( $12.7 \pm 6.5$  seconds) than in those who did not fall ( $5.98 \pm 2.12$  seconds), ( $p=0.009$ ). Notably, however, these individuals also had the greatest improvement with the intervention. After 16 weeks of MMBI scores on the functional gait assessment (FGA) increased by 12% and the time to complete the FSST decreased by 24%. Individuals with FSST > 10 seconds at baseline made even greater improvements of 40-50% on the FSST and FGA. Furthermore these improvements were maintained for 4 months after the completion of the exercise program. These findings warrant the application of our MMBI program to a larger study of greater duration with an active comparison group, particularly in those with a FSST > 10 seconds at baseline.

Parameter (N=16)	Baseline (mean $\pm$ SD)	16 week Post-intervention(mean $\pm$ SD)	P value
BMI (kg/m  )	26.9 $\pm$ 3.2	27.0 $\pm$ 3.2	0.40
Four-square (sec)	8.5 $\pm$ 5.3	6.1 $\pm$ 2.7	0.04
Functional gait assessment*	22.7 $\pm$ 5.9	25.5 $\pm$ 5.2	0.01
Leg extension strength	278.80 $\pm$ 110.5	299.00 $\pm$ 114.9	0.05

\*N of 8, measurement only performed on second cohort

### Methods/Study Procedures:

Approach: We will enroll 56 older community dwelling veterans (age > 65 years) with a fall in the past year and evidence of balance dysfunction (FSST > 10 seconds). Our preliminary findings suggest that those with higher FSST benefit the most from MMBI. After baseline testing, individuals will be randomized to either MMBI or to a Tai Chi intervention. All participants will participate in a group exercise class in their assigned intervention for 1 hour, 3 times per week for 24 weeks. To promote camaraderie and accountability among subjects they will be enrolled in intervention cohorts of 8 to 10 subjects. At randomization subjects will be stratified first by gender then by FSST. Assessments will occur at baseline and after completion of the intervention and will include balance, mobility and fall risk, lower extremity strength, and muscle composition (total body DXA scan, hip and thigh CT scan). All participants will be followed from initial enrollment until 6 months after completion of the post-intervention testing (6 months follow up) utilizing calendar diaries, post-cards and monthly phone calls from the study coordinator to determine the number of falls, near falls, injuries and fall related medical visits.

Recruitment and Screening: A variety of methods will be used to recruit older veterans with a history of a fall in the last year, including the Baltimore GRECC subject recruitment registry, advertisements, provider referrals, community outreach, outpatient clinics and the emergency department at the VAMHCS. The use of multiple recruitment strategies will allow us to maximize our outreach to a diversity of veterans including those who have yet to seek routine care at the VA. A fall will be defined as any event that resulted in a person coming to rest unintentionally on the ground or other lower level. Prospective studies have demonstrated that older adults with a history of falls are more likely to experience subsequent falls. Exclusion criteria will include: dementia, unstable angina, poorly controlled hypertension, active substance abuse, poorly controlled diabetes, progressive neurodegenerative disease, and any other major orthopedic or health condition that would limit ability to safely exercise (see human subjects section for more

details). Interested individuals will initially undergo a telephone screen by the project coordinator to assess eligibility for the study using our inclusion/exclusion criteria. Potential participants who pass the phone screen will be invited to our facility. After informed consent, a history and physical will be performed. Based on prior studies we anticipated that 20 to 30% of those brought in for the screening evaluations will not qualify for the study (screening failures).

After the completion of all screening tests eligible participants will be scheduled for baseline testing at the Baltimore GRECC and VAMHC Human Performance Laboratory consisting of: 1) balance testing (Four-square step test), 2) mobility and fall risk assessment (functional gait assessment, clinical gait assessment and gait variability on a GAITrite and 6 minute walk), 3) questionnaires (falls efficacy and ABC) 4) lower extremity isometric strength testing (Biodex), and 6) total body DXA scan, and a CT scan of the abdomen, hips and thighs for determination of lower extremity and core muscle composition. All testing will be conducted by individuals that are blinded to group assignment and not involved with group training.

After completion of baseline testing the veterans will be randomized to either MMBI or a Tai Chi intervention. The MMBI and Tai Chi intervention sessions will be held at different times of the day to minimize cross-contamination between the two groups, with time alternating with different cohorts to minimize any inadvertent training effect due to time of day.

The supervised Tai Chi class will be held 3-times a week for one hour. All Tai Chi classes will be taught in a group setting by an experienced instructor and will have a maximum instructor to participant ratio of 10:1. The Tai Chi intervention will be modeled after the Tai Chi Moving for Better Balance Program (TJQMBB). This specific Tai Chi program is a 24 week established nationwide Tai Chi program aimed at individuals with balance disorders. TJQMBB is a research based balance training regimen with clinical efficacy per the CDC. Using this program will allow us a specific progression of exercises in Tai Chi with a focus on stimulating musculoskeletal, sensory, and cognitive systems via self-initiated, controlled movements such as unilateral weight-bearing and weight-shifting, trunk rotation, ankle sways, and coordinated eye-head-hand movements, and taxing sensory integration, limits of stability, functional adaptation, anticipatory control, compensatory responses, and effective gait patterns. Movements will be adapted as the class progresses to increase the difficulty of weight shift and change in direction over time so that participants balance is continually challenged throughout the 24 weeks. Because all participants will be at high risk for falls in addition to the Tai Chi instructor 1-2 assistants will be present to assist with fall risk prevention and chairs or hand rails will be present for the participants to use as needed for balance recovery.

The MMBI will be held 3-times a week for an hour and will consist of a group dynamic balance class (30 minutes), a supervised obstacle course (10 minutes), and lower extremity and core strengthening (20 minutes). The group exercise class will focus on dynamic weight shifts with an emphasis on the lateral and diagonal directions. Over the 24 weeks of class the exercises will gradually increase in difficulty to challenge balance. A skilled instructor will lead each class and 1-2 assistants will be present to assist with fall risk prevention. The supervised obstacle course will focus on obstacle negotiation, gait over challenging surfaces, and moving in lateral, diagonal, and backward directions. Strength training of the lower extremities and core will focus on strengthening the major muscles of the lower extremity and core (hip flexor/extensors, hip abductors/adductors, knee flexor/extensors, ankle plantar flexor/dorsiflexors, ankle invertors/evertors, and core abdominal/back extensor muscles) utilizing commonly available gym equipment, ankle weights and body weight. Because our group program will utilize commonly available equipment for both the balance training and the strengthening portion our MMBI can be easily implemented in a community environment.

After completion of the intervention, subjects will repeat the baseline assessments. The testers will be blinded to group assignment. All participants will be encouraged to continue performing their exercises at home (home maintenance). They will be followed for an additional

6 months after completion of testing utilizing post-cards and monthly phone calls from the coordinator to determine the number of falls, near falls, injuries and fall related medical visits.

Aim 1: Primary Outcome Measures: Four-Square Step Test (FSST) and Functional Gait Assessment Tests (FGA). The primary outcome measures will be the change from baseline to 24 weeks in the FSST and the FGA. The FSST is a test of dynamic balance ability that assesses an individual's ability to change directions while stepping. Subjects will be timed as they step over four canes set-up in a cross on the floor. Participants will be closely guarded as they perform the test to prevent any falls. The FSST is an ideal outcome measure as it assesses the ability of an individual to dynamically maintain an upright posture while changing directions and weight shifting. It has excellent inter-rater reliability (ICC=0.99), test-retest reliability (ICC=.98), sensitivity (92%) and specificity (93%) in older adults. Older adults who take > 15 seconds to complete the task are at increased risk for multiple falls.

The FGA will also be used as a primary measure of dynamic mobility and balance and to assess fall risk. The FGA is a 10-item clinical gait test that is based on the dynamic gait index (DGI). It tests higher level dynamic gait activities that are part of daily functional mobility such as turning safely, walking at speeds required to safely cross a street, the ability to walk with head turns, gait with a narrow base of support and ambulating backwards. Each of the ten items is scored 0 to 3, with total scores ranging from 0 to 30. Scores below 22 are predictive of future falls. The FGA has excellent inter-rater reliability (ICC=.93) and predictive validity for falls. The FGA is an ideal outcome for this balance study in older veterans.

